3.7.1.2 Secondary Safety Endpoints

Safety will be assessed by the documentation of all adverse events throughout the study. Serious adverse events will be reported, as appropriate. Twelve lead ECG will be performed during all scheduled study Visits (including an early termination Visit, if one happens) to screen for prolongation of the QT interval. In addition, the following Scales will be assessed:

- 1. Columbia Suicide Severity Rating Scale.
- 2. Stanford Sleepiness Scale.
- 3. Mini Mental Scale.
- 4. MDS-Unified Parkinson's Disease Rating Scale.
- 3.7.2 Efficacy Endpoints

3.7.2.1 Primary Efficacy Endpoint

The AUDYT trial will be a patient-driven study. Accordingly, the primary efficacy endpoint will be patient-driven as well: during Visit 4, study subjects will be administered the Patient Global Impression of Improvement Scale (PGI-I), with which they will quantify the degree of change (if any) in their dystonic symptoms that is attributable to their participation in the trial. The median of all of these assessments will be considered the primary efficacy endpoint.

3.7.2.2 Secondary Efficacy Endpoints

The secondary efficacy endpoints will be:

- the median of all CGI-I
- within subjects paired t-tests to assess significance of change in the GDS between Visits 1 and 4.

Both the CGI-I and GDS will be extracted by blinded raters who will evaluate video examinations of the study subjects following an established protocol, as mentioned elsewhere in this document.

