2.4 Efficacy Outcome Assessments

Although the AUDYT trial is not powered to accurately establish efficacy of AUSTEDO, the following assessments will be performed:

- Patient Global Impression of Improvement: During Visit 4, subjects will be asked to rate the change in their dystonic symptoms using this Scale.
- Clinical Global Impression of Improvement Scale: A video will be made of each subject's movement disorder examination during Visits 1 and 4. Videos will be sent to raters blinded to Visit number and recording date. Raters will be asked to compare the videos looking for any change in the subjects' dystonic symptoms. Their impressions will be recorded using this Scale.
- Global Dystonia Rating Scale: Blinded video raters will also be asked to rate the severity of the subjects' dystonia in all videos using this Scale.

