3.5.2.5 Subject Withdrawal

Subjects will be advised that they are free to withdraw from the study at any time. Reasons that subjects may be withdrawn from the study include the following:

• Subject discontinued study medication: according to the package insert,³ following treatment interruption of greater than one week, AUSTEDO therapy would need to be re-titrated when resumed, and, thus, subjects who require drug cessation for a week or more will be considered

withdrawn from the trial. For treatment interruption of less than one week, treatment can be resumed at the previous maintenance dose without titration, as per the package insert.³

- Subject consent is withdrawn
- QTc changes: A study subject will be asked to discontinue study drug if at any point during the trial he or she is found on ECG to have developed a QTc> 500 milliseconds or a QTc increase of >60 milliseconds from baseline.
- Sponsor decision, after discussion with the Investigator

If a subject is withdrawn from the study, all efforts will be made to complete the early termination Visit that includes efficacy assessments and safety follow-up. In addition, women of childbearing potential will have a pregnancy test performed at the early termination Visit. All information, including the reason for withdrawal, will be reported. For subjects who are lost to follow-up, three recorded attempts will be made to contact the subject for follow-up information, including reason for discontinuation and follow-up of AEs. Subjects who withdraw from the study will not be replaced.

- 3.6 Study Procedures and Assessments
- 3.6.1 Safety assessments
- 3.6.1.1 Adverse Events

During the study, the Investigator or study site personnel will be responsible for querying and recording adverse events (AEs) and serious adverse events (SAEs). In this study AEs and SAEs will be reported from the time of study drug administration until Visit 5 or death, whichever occurs first.

An adverse event (AE) is any untoward medical occurrence that occurs in conjunction with the use of a medicinal product in humans, whether or not considered to have a causal relationship to the medicinal product. According to the package insert,³ adverse reactions experienced by at least 4% of subjects on AUSTEDO and with a greater incidence than on placebo include somnolence, diarrhea, dry mouth, fatigue, urinary tract infection, insomnia, anxiety, constipation and contusion.

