3.6.2.2 Patient Global Impression of Improvement Scale

During Visit 4, subjects will be asked to assess their dystonic symptoms using the Patient Global Impression of Improvement Scale (PGI-I). Figure 8 shown below shows this Scale embedded in a data capture form:

Date: DD – MMM – YYYY	Study subject number:
Visit Number 4	

The AUDYT Trial Patient Global Impression of Improvement

Please check the one number that best describes how your dystonia is now compared to when you started your participation in the AUDYT trial:

- 1 Very much better
- 2 Much better
- 3 A little better
- 4 No change
- 5 A little worse
- 6 Much worse
- 7 Very much worse

Raters will be provided 2 videos for every study subject: one recorded during Visit 1, and another recorded during Visit 4. Videos will be randomly labeled as Video A and Video B for each subject, but the letter assigned will have no correlation with the order in which the videos were captured. The raters will be asked to make a global comparison of both videos, and to record their assessment using the form shown in Figure 9 below:

Date: DD - MMM - YYYY	Study subject number:

To be filled out by blinded video rater

The AUDYT Trial Clinical Global Impression of Improvement Scale

Please select the option that best describes the change in this subject's dystonia between videos A and B:

1	This subject's dystonia is very much better in Video A compared to Video B
2	This subject's dystonia is much better in Video A compared to Video B
3	This subject's dystonia is a little better in Video A compared to Video B
4	This subject's dystonia is unchanged between Videos A and B
5	This subject's dystonia is a little better in Video B compared to Video A
6	This subject's dystonia is much better in Video B compared to Video A
7	This subject's dystonia is very much better in Video B compared to Video A

Besides performing CGI-I for the videos, raters will be ask to evaluate the severity of the dystonia in each video supplied. The Dystonia Study Group developed the Global Dystonia Rating Scale (GDS) to serve as an instrument to assess dystonia severity. Figure 10 shown below shows the Global Dystonia Rating Scale²¹ embedded in a data capture form:

Figure 11

Date: DD – MMM – YYYY Study subject number: _____

Please circle the video for which this form is used:
Video A Video B

The AUDYT Trial Global Dystonia Rating Scale

BODY REGION SCORED	CLINICAL NOTES (Optional)		ore 10)		
EYES & UPPER FACE					

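### Does section 3.7.2.2 need a written rule for turning the blinded raters' video forms into one value per subject?

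*Combined protocol and SAP*

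**What the plan says.** Section 3.7.2.2 lists two secondary efficacy endpoints. One is "the median of all CGI-I". The other is a paired t-test within subjects for the "significance of change in the GDS between Visits 1 and 4". Blinded raters produce both from the video examinations.

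The rating procedure is in the text that follows section 3.6.2.2 (sections 3.6.2.3 and 3.6.2.4 in the table of contents). It says "Raters will be provided 2 videos for every study subject", one from Visit 1 and one from Visit 4. The two are lettered A and B at random, and "the letter assigned will have no correlation with the order in which the videos were captured". The CGI-I form is a seven-point comparison of the lettered videos. Score 1 means the "dystonia is very much better in Video A compared to Video B", 4 means unchanged, and 7 is the mirror image of 1. For the GDS, "raters will be ask to evaluate the severity of the dystonia in each video supplied", on a form that is also marked A or B and not by visit. Section 2.4 says much the same: "Blinded video raters will also be asked to rate the severity" of dystonia in all the videos.

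No section gives the number of raters per subject, a rule for combining raters, or an explicit recoding of the CGI-I to visit order. Section 6 defines the analysis populations and the handling of deviations, and adds nothing on these points.

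**The concern.** Two steps between the forms and the endpoints are unwritten.

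The first is decoding. A raw CGI-I score says which letter looks better, and the letter is random. A median of raw scores would therefore say nothing about improvement.

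The second is the rater rule. The text speaks of raters in the plural and can be read as giving every rater every subject. If so, each subject has one CGI-I score and one GDS change per rater. The CGI-I median could then run over all forms or over one score per subject. The GDS test could use per-subject averages, treat each rater's pair as an independent observation, or be run once per rater. The last two would inflate the false-positive rate of the only significance test that section 3.7 attaches to an efficacy endpoint. A choice among the three made after the key is opened could change the reported p-value.

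**Working it through.** The plan gives no figure to reproduce. The 15 subjects were set by recruitment (section 3.3), and no significance level, effect size, standard deviation or rater count is stated.

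**Decoding.** Let s be the form score. If Video A is the Visit 4 video, keep s; otherwise use 8 − s. A subject much better at Visit 4 scores 2 when Visit 4 is Video A. When Visit 4 is Video B the score is 6, and 8 − 6 = 2.

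Take 15 subjects who are all much better, with letters assigned 50/50:

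- The decoded median is 2.
- The raw median is 2 if at least 8 of the 15 have Visit 4 as Video A, and 6 otherwise. Each has probability 0.5.

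Now take an assumed mixed profile of 5, 25, 40, 20 and 10% at scores 1 to 5. The decoded median falls below 4 in 95% of simulated trials and the raw median in 21%, with the raw median averaging 4.0. The undecoded median is thus unusable as a measure of improvement. The other secondary endpoint cannot be computed at all without the same key, because its forms are also lettered and its comparison is between visits. The key must therefore exist and be applied.

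**Raters.** Assumptions, none from the documents: 15 subjects, R raters each scoring every subject, normal GDS changes with variance 1, correlation r between raters' changes, no true change, two-sided 5% test.

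With per-subject averages, the 15 averages are independent. The t-test on 14 degrees of freedom is exact at 5% for any R and r (simulated 4.9 to 5.0%).

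With pooled pairs, the true variance of the mean is a/(15R), where a = 1 + (R − 1)r, but the test takes it to be about 1/(15R). For R = 2 and r = 0.5, a = 1.5, so the standard error is too small by a factor of about √1.5 = 1.22. For R = 3 and r = 0.9, a = 2.8 and the factor is about √2.8 = 1.67. The exact form is T = Z√a / √{[a·χ²(14) + (1 − r)·χ²(15(R − 1))]/(15R − 1)}, compared with the t critical value on 15R − 1 degrees of freedom. The last two columns below come from simulation of the separate tests.

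| r | Pooled, R = 2 | Pooled, R = 3 | At least one rater significant, R = 2 | At least one, R = 3 |
|---|---|---|---|---|
| 0.3 | 8.6% | 12.2% | 9.5% | 13.7% |
| 0.5 | 11.1% | 16.9% | 9.2% | 12.8% |
| 0.7 | 13.8% | 21.4% | 8.6% | 11.2% |
| 0.9 | 16.4% | 25.5% | 7.1% | 8.5% |

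With 12 subjects the pooled figures move by less than 0.5 percentage points. With R = 1 all three analyses coincide and there is no effect.

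**Which analysis does the text describe?**

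- Section 3.7.2.2 and the synopsis both call for a paired test within subjects. A test on 30 or 45 rater-level rows fits that description poorly.
- The plural in t-tests does not imply one test per rater. In the synopsis (Statistical Methods) the same tests are applied to several scales.
- Section 3.7.2.1 uses a parallel wording for the PGI-I, the median of all the assessments, where there is plainly one score per subject.
- The CGI-I form is headed for completion by a single rater. That does not settle the number per subject, but plural raters also fits a panel that divides the subjects among its members.

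**The case for a change.** The strongest reply is that the rater gap, unlike the decoding gap, is not filled by anything else in the plan. The text can fairly be read as every rater scoring every subject, since the raters receive two videos for each subject and section 2.4 has them rate all videos. On that reading some combining rule is needed, none is given, and one sentence would supply it at no cost.

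It stands that neither the number of raters nor a combining rule is stated. It does not follow that the planned analysis is wrong. The inflated error rates need several raters per subject, which is not established, and a pooled or per-rater test, which no section describes. With several raters, a statistician given a within-subject paired test would reduce the scores to one value per subject and visit, and the level then holds. Mean, median or consensus could give slightly different estimates, but any of them fixed before decoding keeps the subject as the unit.

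A related question is whether a video from "the early termination Visit that includes efficacy assessments and safety follow-up" may serve as the second video, since section 6.1.2 requires both examinations. That concerns missing data, not the combining of forms. Section 3.7.2.2 names Visits 1 and 4 for the GDS, and the rater instructions name the videos from the same two visits.

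**Conclusion.** No change follows. The decoding is implied by the scale's purpose, by the objective of measuring effect after six weeks at dose, and by the GDS comparison between visits, which needs the same key. Writing it down would not alter the result. The rater rule is missing detail that analysts would fill sensibly with one value per subject. On that basis the GDS test holds 5% for any number of raters, given independent subjects and normal changes.

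The figures of up to 25.5% describe an analysis that the plan does not state, under an assumed rater count, correlation and significance level. The stakes are also small: these are secondary efficacy endpoints in a 15-subject open-label pilot that the synopsis and section 2.4 describe as not powered for efficacy. The conclusion would differ only if the analysts intended to treat several raters' scores on one subject as independent pairs, and nothing in the documents suggests that.

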3.8 Criteria for Study Termination

The Sponsor reserves the right to discontinue the trial at any time; reasons will be provided in the event of this happening. The Principal Investigator reserves the right to discontinue participation in the study for safety or other reasons at any time in collaboration with the Sponsor. The Investigator will notify the IRB/REC/IEC in writing of the trial's completion or early termination and provide a copy of the notification to the Sponsor.

- 4. STUDY DRUG MATERIALS AND MANAGEMENT
- 4.1 Study Drug
- 4.1.1 Description

As described in the drug's package insert,³ AUSTEDO (AUSTEDO) is a vesicular monoamine transporter 2 (VMAT2) inhibitor for oral administration. The molecular weight of AUSTEDO is 323.46; the pKa is 6.31. AUSTEDO is a hexahydro-dimethoxybenzoquinolizine derivative and has the following chemical name: (RR, SS)-1, 3, 4, 6, 7, 11b-hexahydro-9, 10-di(methoxy-d3)-3-(2-methylpropyl)2H-benzo[a]quinolizin-2-one. The molecular formula for AUSTEDO is $C_{19}H_{21}D_6NO_3$. AUSTEDO is a white to slightly yellow crystalline powder that is sparingly soluble in water and soluble in ethanol.

AUSTEDO tablets contain 6 mg, 9 mg, or 12 mg AUSTEDO, and the following inactive ingredients: ammonium hydroxide, black iron oxide, n-butyl alcohol, butylated hydroxyanisole, butylated hydroxytoluene, magnesium stearate, mannitol, microcrystalline cellulose, polyethylene glycol, polyethylene oxide, polysorbate 80, polyvinyl alcohol, povidone, propylene glycol, shellac, talc, titanium dioxide, and FD&C blue #2 lake. The 6 mg tablets also contain FD&C red #40 lake. The 12 mg tablets also contain FD&C yellow #6 lake. Only 6 mg AUSTEDO tablets will be used in the AUDYT trial.

4.1.2 Mechanism of action

According to the package insert,³ the precise mechanism by which AUSTEDO (AUSTEDO) exerts antichorea effects is unknown but is believed to be related to its effect as a reversible depletor of monoamines (such as dopamine, serotonin, norepinephrine, and histamine) from nerve terminals. The major circulating metabolites (α -dihydrotetrabenazine [HTBZ] and β -HTBZ) of AUSTEDO, are reversible inhibitors of VMAT2, resulting in decreased uptake of monoamines into synaptic vesicles and depletion of monoamine stores.

4.1.3 Pharmacodynamics

The following considerations are mentioned in AUSTEDO's package insert:³

Cardiac Electrophysiology

The effect of a single 12-mg or 24-mg dose of AUSTEDO on the QT interval was studied in a randomized, double-blind, placebo-controlled crossover study in healthy male and female subjects with moxifloxacin as a positive control. At 24 mg, AUSTEDO caused an approximately 4.5 milliseconds mean increase in QTc (90% CI: 2.4, 6.5 msec). Effects at higher exposures to AUSTEDO or its metabolites have not been evaluated. The effect of a single 25-mg or 50-mg dose of tetrabenazine, a closely related VMAT2 inhibitor, on the QT interval was studied in a randomized, double-blind, placebo-controlled crossover study in healthy male and female subjects with moxifloxacin as a positive control. At 50 mg, tetrabenazine caused an approximately 8 milliseconds mean increase in QTc (90% CI: 5.0, 10.4 msec). Effects at higher exposures to either tetrabenazine or its metabolites have not been evaluated.

Melanin Binding

AUSTEDO or its metabolites bind to melanin-containing tissues (i.e., eye, skin, fur) in pigmented rats. After a single oral dose of radiolabeled AUSTEDO, radioactivity was still detected in eye and fur at 35 days following dosing.

4.1.4 Pharmacokinetics

As stated in the drug's package insert,³ after oral dosing up to 25 mg, plasma concentrations of AUSTEDO are generally below the limit of detection because of the extensive hepatic metabolism of AUSTEDO to the active deuterated dihydro metabolites (HTBZ), α -HTBZ and β -HTBZ. Linear dose dependence of Cmax and AUC was observed for the active metabolites following single or multiple doses of AUSTEDO (6 mg to 24 mg and 7.5 mg twice daily to 22.5 mg twice daily).

Absorption

Following oral administration of AUSTEDO, the extent of absorption is at least 80%. Plasma concentrations of AUSTEDO are generally below the limit of detection after oral dosing. Peak plasma concentrations (Cmax) of deuterated α -HTBZ and β -HTBZ are reached within 3 to 4 hours after dosing.

Effect of Food

The effects of food on the bioavailability of AUSTEDO were studied in subjects administered a single dose with and without food. Food had no effect on the area under the plasma concentration-time curve (AUC) of α -HTBZ or β -HTBZ, although Cmax was increased by approximately 50% in the presence of food.

Distribution

The median volume of distribution (Vc/F) of the α -HTBZ, and the β -HTBZ metabolites of AUSTEDO are approximately 500 L and 730 L, respectively. Results of PET-scan studies in humans show that following intravenous injection of 11C-labeled tetrabenazine or α -HTBZ, radioactivity is rapidly distributed to the brain, with the highest binding in the striatum and lowest binding in the cortex. The in vitro protein binding of tetrabenazine, α -HTBZ, and β -HTBZ was examined in human plasma for concentrations ranging from 50 to 200 ng/mL. Tetrabenazine binding ranged from 82% to 85%, α -HTBZ binding ranged from 60% to 68%, and β -HTBZ binding ranged from 59% to 63%.

Elimination

AUSTEDO is primarily renally eliminated in the form of metabolites. The half-life of total ($\alpha+\beta$)-HTBZ from AUSTEDO is approximately 9 to 10 hours. The median clearance values (CL/F) of the α -HTBZ, and the β -HTBZ metabolites of AUSTEDO are approximately 47 L/hour and 70 L/hour, respectively, in the Huntington's disease patient population.

Metabolism

In vitro experiments in human liver microsomes demonstrate that AUSTEDO is extensively biotransformed, mainly by carbonyl reductase, to its major active metabolites, α -HTBZ and β HTBZ, which are subsequently metabolized primarily by CYP2D6, with minor contributions of CYP1A2 and CYP3A4/5, to form several minor metabolites.

Excretion

In a mass balance study in 6 healthy subjects, 75% to 86% of the AUSTEDO dose was excreted in the urine, and fecal recovery accounted for 8% to 11% of the dose. Urinary excretion of the $\alpha\textsc{-HTBZ}$ and $\beta\textsc{-HTBZ}$ metabolites from AUSTEDO each accounted for less than 10% of the administered dose. Sulfate and glucuronide conjugates of the $\alpha\textsc{-HTBZ}$ and $\beta\textsc{-HTBZ}$ metabolites of AUSTEDO, as well as products of oxidative metabolism, accounted for the majority of metabolites in the urine.

4.2 Study Drug Packaging and Labeling

As mentioned in the package insert,³ AUSTEDO tablets are available in the following strengths and packages: 6 mg: round, purple-coated tablets, with "SD" over "6" printed in black ink on one side. Bottles of 60 tablets: NDC 68546-170-60. 9 mg: round, blue-coated tablets, with "SD" over "9" printed in black ink on one side. Bottles of 60 tablets: NDC 68546-171-60. 12 mg: round, beige-coated tablets, with "SD" over "12" printed in black ink on one side. Bottles of 60 tablets: NDC 68546-172-60. Only 6 mg AUSTEDO tablets will be used in the AUDYT trial.

4.3 Study Drug Storage

As per the package insert,³ AUSTEDO will be stored at 25° C (77°F); excursions permitted to 15°C to 30°C (59°F to 86°F). It will be protected from light and moisture.

- 4.4 Administration
- 4.4.1 Route of Administration and Dose Schedule

According to the package insert,³ the dose of AUSTEDO is determined individually for each patient with Huntington's Disease based on reduction of chorea and tolerability. When first prescribed to subjects who are not being switched from tetrabenazine (a related VMAT2 inhibitor), the recommended starting dose of AUSTEDO is 6 mg administered orally once daily. The dose of AUSTEDO may be increased at weekly intervals in increments of 6 mg per day to a maximum recommended daily dosage of 48 mg. Total daily dosages of 12 mg or above will be administered in two divided doses. AUSTEDO will be administered with food. AUSTEDO will be swallowed whole. It will not be chewed, crushed or broken.

Based on these recommendations (and as shown in Table 3 below), for the purpose of the AUDYT trial, each study subject is expected to start, increase, maintain and then discontinue AUSTEDO 6 mg tablets as follows:

Table 3
Expected study drug titration for subjects able to increase AUSTEDO to 48 mg/day

				Total	Total
		Number of		number of	number of
	Number of	afternoon	Total daily	tablets per	tablets per
	morning tablets	tablets	dose (mg)	day	week
Week 1	1	1	12	2	14
Week 2	1	2	18	3	21
Week 3	2	2	24	4	28
Week 4	2	3	30	5	35
Week 5	3	3	36	6	42
Week 6	3	4	42	7	49
Week 7	4	4	48	8	56
Week 8	4	4	48	8	56
Week 9	4	4	48	8	56
Week 10	4	4	48	8	56
Week 11	4	4	48	8	56
Week 12	4	4	48	8	56
Week 13	0	0	0	0	0

Table 4 below shows how subjects receiving a strong CYP2D6 inhibitor will start, increase, maintain and then discontinue AUSTEDO 6 mg tablets:

Table 4
Expected study drug titration for subjects able to increase AUSTEDO to 36 mg/day

				Total	Total
		Number of		number of	number of
	Number of	afternoon	Total daily	tablets per	tablets per
	morning tablets	tablets	dose (mg)	day	week
Week 1	1	1	12	2	14
Week 2	1	2	18	3	21
Week 3	2	2	24	4	28
Week 4	2	3	30	5	35
Week 5	3	3	36	6	42
Week 6	3	3	36	6	42
Week 7	3	3	36	6	42
Week 8	3	3	36	6	42
Week 9	3	3	36	6	42
Week 10	3	3	36	6	42
Week 11	0	0	0	0	0

In subjects receiving a strong CYP2D6 inhibitor, the ramp-up period will be reduced to 4 weeks, reducing the duration of their participation in the study to 11 weeks.

